6.1.1 Medical Devices

Medical device (not manufactured by the Sponsor) provided for use in this study is the [REDACTED]

Instructions for medical device use are provided in the product insert.

[figure not shown]
[figure not shown]
[REDACTED]

[REDACTED]

[REDACTED]

[REDACTED]

[REDACTED]

In vitro device performance characterization:

[REDACTED]

6.2 Preparation, Handling, Storage, and Accountability

- 1) The investigator or designee must confirm appropriate temperature conditions have been maintained during transit for all study intervention received and any discrepancies are reported and resolved before use of the study intervention.
- 2) Only participants enrolled in the study may receive study intervention and only authorized site staff may supply or administer study intervention. All study intervention must be stored in a secure, environmentally controlled, and monitored (manual or automated) area in accordance with the labeled storage conditions with access limited to the investigator and authorized site staff.
- 3) The investigator, institution, or the head of the medical institution (where applicable) is responsible for study intervention accountability, reconciliation, and record maintenance (ie, receipt, reconciliation, and final disposition records).
- 4) Further guidance and information for the final disposition of unused study interventions will be provided to the study personnel.

6.3 Measures to Minimize Bias: Randomization and Blinding

6.3.1 Randomization and Allocation Procedures

Site staff will connect to the Interactive Response Technology (IRT), enter the identification and security information, and confirm a minimal amount of data in response to IRT prompts. For all participants, the IRT will assign a participant number. For pediatric participants, the IRT will then provide the group assignment and have the site staff confirm it. If the participant is not eligible to participate in the study, then the information will only be recorded on the participant recruitment log.

Participant numbers that are assigned by the IRT will consist of a 12-digit string (a 3-digit country identifier, a 4-digit study center identifier, and a 5-digit participant identifier).

The first digit of the 5-digit participant identifier will correspond to the participant group (ie, 0 for pediatric participants and 1 for ad-hoc close contact participants). For the pediatric participants only, the 2nd and 3rd digits of the participant identifier will correspond to the group of contact identifier. For example, Participant 630000101235 is the 35th participant enrolled in Center Number 1 (630 being Puerto Rico country code) and is part of Contact Group Number 12;

Participant 630000110024 is the 24th ad-hoc close contact participant enrolled in Center Number 1.

Participant numbers should not be reassigned for any reason. The randomization codes will be kept securely in the IRT and an internal system.

6.3.2 Blinding and Code-breaking Procedures

The study will be performed in a modified double-blind fashion:

- Participants, participants' parents or legally acceptable representative, Investigators and study staff who conduct the safety and immunogenicity assessments will not know which study intervention is administered
- Only the study staff who prepare and administer the study intervention and are not involved with the safety evaluation will know which study intervention is administered

The Investigator responsible for safety assessment will not attend the vaccination session but will be available in case of emergency (anaphylactic shock).

Treatment ID numbers will be used to identify each vaccine dose for the purpose of randomization, vaccination, and the recording of the study intervention administered. Treatment numbers will be randomly assigned to study interventions. The IRT vendor will be responsible for assigning the treatment group identification and treatment number to be received by the enrolled pediatric participant. The participant, the participant's parent(s)/legally acceptable representative, the Investigator, and the study staff members who collect the safety data and laboratory personnel who analyze the blood samples will all be blinded to the group assignment. The individual responsible for preparing / administering study intervention will not be authorized to collect any safety / serology data.

The code may be broken in the event of an AE only when the identification of the study intervention received could influence the treatment of the participant. Code-breaking should be limited to the pediatric participant(s) experiencing the AE.

The blind can be broken by the investigator or a designee through the IRT system. Once the emergency has been addressed by the site, the investigator or a designee must notify the Sponsor's RMO if a participant's code was broken. All contact attempts with the Sponsor prior to unblinding are to be documented in the source documents, and the code-breaking case report form (CRF) is to be completed.

The Independent Ethics Committees (IEC) / Institutional Review Boards (IRB) must be notified of the code-breaking, in accordance with local regulations. All documentation pertaining to the event must be retained in the site's study records and in the Sponsor's files. Any intentional or unintentional code-breaking must be reported, documented, and explained, and the name of the person who requested it must be provided to the Sponsor.

A request for the code to be broken may also be made:

- by the Global Pharmacovigilance (GPV) Department through an internal system for reporting to Health Authorities in the case of an unexpected SAE considered causally related, as described in International Council for Harmonisation (ICH) E2A. In this case,

the code will be broken only for the participant(s) in question. The information resulting from code-breaking (ie, the participant's study intervention or group assignment) will not be communicated to either the investigator or the immediate team working on the study, except for the GPV representative.

An unblinded interim analysis will be performed in Q4, 2023 on available data collected from D01 (V01) to D22 (V07), irrespective of study enrollment status. An additional unblinded interim analysis will be performed once all data collected from D01 (V01) to D22 (V07) from all participants is available. The interim analyses will include baseline immunogenicity, safety, and shedding / transmission up to 21 days after the first administration, in order to share preliminary data to Health Authorities.

Randomization code will be broken for the Sponsor but blinding will be maintained at sites and participants/parents levels.

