Control method	Placebo-controlled
Study population	
• Pediatric participants: Healthy infants / toddlers 6 to < 24 months of age in close contact with other infants / toddlers 6 to < 24 months of age who participate in the study• Ad-hoc close contact participants: ad-hoc close contact children and adults who experience acute respiratory illness (ARI) in the 28 days following the administration of the study intervention to the close contact pediatric participant
Countries	United States and Puerto Rico
Level and method of blinding	Observer-blind: 
• Blinding for vaccine group assignment: participants, parents or legally acceptable representative (LAR), outcome assessors, investigators, laboratory personnel, Sponsor study staff• No blinding for study staff who prepare and administer the study interventions
Study intervention assignment method	Pediatric participants will be screened for eligibility criteria at the time of inclusion and randomized to receive either RSVt vaccine or placebo in a 1:1 ratio

Brief Summary:

The primary purpose of the VAD00014 study is to assess the shedding, transmission, and genetic stability of the live-attenuated RSVt vaccine after each intranasal vaccination (56 days apart) in infants and toddlers 6 to < 24 months of age. Study details include:

The study duration will be:

- up to 8 months, including the 6 months safety follow-up phone call after the second study intervention administration for the pediatric participants

The treatment administration for the pediatric participants will be on D01 and D57 (1 intranasal administration each).

The visit frequency will be twice a week after D01 (ie, first administration of study intervention) up to D22 for a total of 7 visits (D01, D04, D08, D11, D15, D18, and D22), and 7, 14, and 28 days after D57 (second administration) at D64, D71, and D85. Some of these visits may be managed as home visits or daycare center visits.

Additional illness visits may occur during the study intervention phase (D01-D85) in case of acute respiratory symptoms.

Number of Participants:

A total of 100 pediatric participants are expected to be randomized (50 participants in each study intervention group).

Intervention Groups and Duration:

Eligible pediatric participants will be randomized in a 1:1 ratio to receive 2 intranasal administrations (56 days apart) of either the RSVt vaccine or placebo at D01 and D57.

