For any pediatric participants presenting clinical symptoms of ARI during the intervention phase (D1 to D85), an additional nasal swab may be collected to identify potential WT RSV infection with Multiplex RT-PCR. Some of the regular nasal swabs from symptomatic children in which no vaccine virus was detected may also be tested for WT RSV strain. If ARI is diagnosed < 2 days before or after a scheduled nasal swab, then the planned nasal swab will be used for WT RT-PCR testing. The ad-hoc close contact participants with any clinical symptoms of ARI within 28 days after study intervention administration of the close contact pediatric participant should have an illness visit.

Consideration of the RSV Season

The VAD00014 study is planned to start during Quarter (Q)4 2022, regardless of the actual start of the RSV season. In the Northern Hemisphere, the RSV season usually begins in late Q3 or early Q4 and lasts about 5 months. However, due to the increased variability in the RSV epidemiology since the beginning of the SARS-CoV-2 pandemic, it is difficult to evaluate the extent to which the RSV season will impact the clinical study. To mitigate the impact of the RSV season during the study, ARI will be followed up to 28 days after the second study intervention administration for all pediatric participants. Baseline blood sample will be used as an indication of possible previous RSV exposure.

Non-exclusion of pregnant women participants

Ad-hoc close contact participants can include pregnant females as they will only provide nasal swabs and will not receive any study intervention. Thus, VAD00014 study can be considered a safety surveillance study for the ad-hoc close contact participants and therefore pregnant women are not excluded from participating in the study.

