10.1.5 Committees Structure

Participant safety will be continuously monitored by the Sponsor's internal safety review committee which includes safety signal detection at any time during the study. The Sponsor's internal safety review committee, led by the PV representative and the RMO and designee(s), will be responsible for the blinded review, assessment, and evaluation of safety data generated from this study. This committee is empowered to recommend a pause in recruitment and/or further vaccination while it investigates any potential signal or concern.

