10.2.3 Recording and Follow-Up of AE and/or SAE

AE and SAE Recording

- When an AE/SAE occurs, it is the responsibility of the investigator to review all documentation (eg, hospital progress notes, laboratory reports, and diagnostics reports) related to the event.
- The investigator will then record all relevant AE/SAE information.
- It is **not** acceptable for the investigator to send photocopies of the participant's medical records to the Sponsor in lieu of completion of the CRF pages.
- There may be instances when copies of medical records for certain cases are requested by the Sponsor. In this case, all participant identifiers, with the exception of the participant number, will be redacted on the copies of the medical records before submission to the Sponsor.
- The investigator will attempt to establish a diagnosis of the event based on signs, symptoms, and/or other clinical information. Whenever possible, the diagnosis (not the individual signs/symptoms) will be documented as the AE/SAE.

Assessment of Causal Relationship

By convention, all AEs reported at the injection site (either solicited or unsolicited) and all solicited systemic AEs are considered to be related to the IMP (see definition in [Section 6](#)) and therefore are referred to as reactions and do not require the investigator's opinion on relatedness.

- Causal relationship of unsolicited systemic AEs and SAEs will be recorded as follows:
 - For non-serious unsolicited systemic AEs (except for non-serious AESIs), relationship to study intervention will usually be assessed by the investigator only.
 - For SAEs and non-serious AESIs, relationship to study intervention will be assessed by both the investigator and the Sponsor (except for injection site reactions which will be related by default). Sponsor assessment is entered in the GPV database only.
 - For SAEs only, the causal relationship to study procedures (related/not related to study procedures) will be assessed by both the investigator and the Sponsor. Sponsor assessment is entered in the GPV database only.
- The investigator will assess the ***causal relationship*** between each unsolicited systemic AE and the study intervention administered as either ***not related*** or ***related***, based on the following definitions:

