### 3.5 Interim Analyses

- An unblinded interim analysis will be performed on available data collected from D01 (V01) to D22 (V07) for participants randomized on or before 21July2023, in two steps:
  - The first step will be performed on available shedding / transmission data by RSVt qRT-PCR assay up to 21 days after the first study intervention administration, that will also include baseline immunogenicity data, safety data up to 21 days after the first study intervention administration, in order to share preliminary data to Health Authorities before moving to phase III clinical development. Randomization code will be broken for the Sponsor but blinding will be maintained at sites and participants/parents levels. Some listings will be generated to define the next steps for nasal swab testing (sequencing, plaque assay and WT RT-PCR).
  - The second step will be performed when subsequent data up to 21 days after the first study intervention administration will be available (e.g. segment sequencing, plaque assay and WT RT-PCR data).
- An additional unblinded interim analysis will be performed once all data collected from D01 (V01) to D22 (V07) from all participants is available. A two-step process of analysis will also be applied.
- The final unblinded statistical analysis will address the objectives on all participants  
No statistical adjustment is necessary because no hypotheses will be tested.  
This study will not include an early safety data review.

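### Sponsor staff are declared blinded throughout, but the code is broken for the Sponsor at two interims during follow-up with no firewall described; the transmission result on the SafAS is not affected

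*Protocol*

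**What the plan says.** **Who is declared blinded.** The blinding row of the Protocol 1.1 synopsis includes "outcome assessors, investigators, laboratory personnel, Sponsor study staff". The design tables in Protocol 4.1 and SAP section 1 repeat this. None gives an end date or an exception for the interims. Protocol 10.1.5 adds that the Sponsor's internal safety review committee, led by the pharmacovigilance (PV) representative and the Responsible Medical Officer (RMO), "will be responsible for the blinded review, assessment, and evaluation of safety data generated from this study".

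**When the code is broken.** Protocol 6.3.2 states: "An unblinded interim analysis will be performed in Q4, 2023 on available data collected from D01 (V01) to D22 (V07), irrespective of study enrollment status". It continues: "An additional unblinded interim analysis will be performed once all data collected from D01 (V01) to D22 (V07) from all participants is available". It then says: "Randomization code will be broken for the Sponsor but blinding will be maintained at sites and participants/parents levels". Protocol 9.4 repeats this. SAP 3.5 restricts the first interim to participants randomized on or before 21 July 2023 and runs each interim in two steps.

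**What is still to be decided afterwards.** Protocol 10.2.3: "For SAEs and non-serious AESIs, relationship to study intervention will be assessed by both the investigator and the Sponsor". SAP 3.5, under the unblinded first step: "Some listings will be generated to define the next steps for nasal swab testing (sequencing, plaque assay and WT RT-PCR". On wild-type testing, Protocol 4.2 says: "Some of the regular nasal swabs from symptomatic children in which no vaccine virus was detected may also be tested for WT RSV strain".

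**The concern.** An unblinded interim in a descriptive study is legitimate, and this one is disclosed with its purpose. The difficulty is that the plan claims a blind which it then gives up without saying for whom. Read literally, breaking the code for the Sponsor includes the RMO and PV representative who lead a committee charged with blinded review, and the staff who assess causality for the Sponsor.

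The documents know how to write a firewall. For a single-case code-break by pharmacovigilance, Protocol 6.3.2 keeps the result from the investigator and the immediate study team. The much larger interim code-break has no such sentence.

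What is at stake is judgement exercised with knowledge of the arm. Such judgements can drift between arms without anyone intending it, and a report could not then describe them as blinded.

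**Working it through.** The plan gives no figure on this point, so the check has three parts.

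**1. Do the interims fall during the trial?**
Inputs: cut date 21 July 2023 (SAP 3.5); first interim in Q4 2023 (Protocol 6.3.2); visits at D22, D57, D85 and D237 (Protocol Table 1.1); SAEs collected to 180 days after the last vaccination (Protocol 8.3.1).
Formula: calendar date = randomization date + (study day − 1).
- A child randomized on 21 July 2023 nominally reaches D22 on 11 August, D57 on 15 September, D85 on 13 October 2023 and D237 on 13 March 2024.
- For that child, Q4 2023 runs from study day 73 to study day 164. SAE follow-up is open throughout. The adverse-event period after dose 2 is also open if the interim falls early in October.
- 31 December 2023 minus 236 days is 9 May 2023. Anyone randomized after 9 May has not reached D237 even if the interim is run on the last day of the quarter.
- First-interim participants should have had dose 2 before Q4 begins (15 September plus the 7-day window is 22 September). Second doses still running at that point would belong to later enrollees, if enrolment is still open.
- The second interim needs only D22 data from everyone. At the earliest it falls 57 − 22 = 35 days before the last participant's dose 2, 85 − 22 = 63 days before D85 and 237 − 22 = 215 days before D237. Assay time will shorten these gaps.

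**2. Which decisions are exposed?**
- *Transmission, SafAS.* Defined as RSVt qRT-PCR at or above the LOD (SAP 4.2.1) on scheduled swabs from all children, with laboratory personnel declared blinded. No PPAS exclusion applies. Not exposed.
- *Transmission, PPAS.* Most criteria are factual: valid swab count and spacing, wrong product at D01, emergency unblinding, and prior RSV exposure (baseline IgA at or above the LOD, SAP 4.2.6.3). Eligibility and preparation or administration deviations need judgement. Nothing fixes membership before code release. Exposed to that extent.
- *Causality.* The Sponsor's assessment is held only in the pharmacovigilance database (Protocol 10.2.3). SAP 4.2.5.5 tabulates the relationship field as collected, and sites remain blinded. The exposure is in safety reporting and signal review, not in the study report tables.
- *Sequencing.* SAP 3.4.2.3 fixes the selection, which needs the allocation by design, and keeps the arm off the laboratory's listing. Not exposed.
- *Wild-type RT-PCR and plaque assay.* Protocol 4.2 has one fixed rule, for an ARI diagnosed less than 2 days from a scheduled swab. Beyond that, wild-type testing of regular swabs is optional, and no complete rule is readable for either assay. Exposed unless a rule is in the redacted text.

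**3. How large could one PPAS decision be?**
Input: 50 placebo children planned (Protocol 9.5). Method: Clopper-Pearson, as in Protocol 9.3.1.
- One positive kept: 1/50 = 2%. Lower limit 1 − 0.975^(1/50) = 0.05%. Upper limit, the 97.5% quantile of Beta(2, 49), = 10.6%.
- That child excluded: the child leaves the denominator too, so 0/49. Upper limit 1 − 0.025^(1/49) = 7.3%.

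**The case against.** The strongest reply is that this is a wording gap with little consequence. No hypothesis is tested, so no alpha is at stake. The primary readout is an objective assay. Protocol section 8 withholds potentially unblinding results from sites and other blinded personnel. Most of this stands and sets the limits of the point. The section 8 safeguard does not close the gap, because it never says who at the Sponsor counts as blinded.

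A reader might infer more than the documents support:
- *That an extra wild-type test could change the transmission result.* Wild-type RT-PCR is not part of the transmission definition.
- *That a PPAS exclusion could remove a transmission from the report.* The primary analysis is also run on the SafAS, where the positive remains.
- *That reported causality is compromised.* The Sponsor's assessment does not feed the SAP tables.
- *That every participant's code is released at the first interim.* SAP 3.5 limits that analysis to D01–D22 data from participants randomized by 21 July 2023, and nothing says later enrollees' codes are released then.
- *That swab selection is left entirely open.* Sequencing is ruled and masked, and a wild-type rule may sit in redacted sections.

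It is also fair to say that no text names who decides PPAS deviations or prepares the listings. That this is the Sponsor is inferred from SAP 3.4.1, which makes its biostatistics group responsible for the analyses.

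**Conclusion.** The contradiction is in the text and nothing readable resolves it. From the first interim, the declared blinding of Sponsor study staff and the blinded remit of the safety committee do not hold for interim participants.

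The effect is modest. It reaches the judgement-based PPAS criteria, pharmacovigilance causality and signal review, and any wild-type or plaque-assay selection not fixed by rule. It does not reach transmission on the SafAS. The move from 1/50 to 0/49 applies to the PPAS only. It assumes exactly one positive and the full planned arm; the real PPAS will probably be smaller, because RSV-exposed children and those with too few swabs are dropped. The documents give no expected number of transmissions.

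The conclusion rests on reading the phrase about the Sponsor as covering the whole organisation, since no narrower group is named, and on the redacted text containing no firewall. It still merits a change, because the remedy is nearly free and the interim data are meant for Health Authorities before Phase III.

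**What to change.** In Protocol 6.3.2 and 9.4 and SAP 3.5:
1. Fix PPAS membership for the participants in each interim before their code is released. Every PPAS criterion concerns eligibility, baseline or the period to D22, so it can be settled from data the interim already needs.
2. Release participant-level codes only to the biostatistics staff who run the interim and prepare the masked swab listings. Keep the RMO, PV causality assessors, safety committee and laboratory blinded at participant level.
3. Select swabs for wild-type RT-PCR and plaque assay by a written rule that does not use the arm, unless the redacted text already contains one.
4. Amend the blinding rows (Protocol 1.1 and 4.1, SAP section 1) and Protocol 10.1.5 to state who is unblinded at each interim. Say whether the safety committee sees group-level tables, since that too departs from a fully blinded review.

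Items 1 and 4 need only wording and sequencing of work. Item 2 restricts access within the Sponsor. Item 3 may add a few tests on stored swabs.
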